5.1 Management of Optical Correction

A refraction should be performed at any time the investigator suspects that refractive error may not be optimally corrected. A change in spectacle correction is at investigator discretion.

5.2 Management of Strabismus

Strabismus surgery should not be done until after the 12-week off-atropine outcome visit has been completed. Surgery will be recorded in the comment section of the Follow-up Examination Form.

5.3 Worsening of Visual Acuity in the Amblyopic Eye

If visual acuity should worsen in the amblyopic eye (or in the sound eye and does not recover with cessation or reversal of treatment), the investigator should evaluate this condition using best clinical judgment and perform whatever work-up is clinically indicated to assess for an alternate cause (i.e., other than amblyopia) for the visual loss. Patients found to have a cause other than amblyopia that fully explains the visual loss (i.e., amblyopia was never present) will be dropped from the study.

5.4 Patient Withdrawals

A parent or guardian may withdraw a patient from the trial at any time. This is expected to be a very infrequent occurrence in this trial in view of the testing procedures' similarity to routine clinical practice. If the parents or guardian indicate that they want to withdraw the child from the study, the investigator should attempt to speak with them to determine the reason.

5.5 Risks

There are no risks involved in this study that would not be part of usual care in which the study treatments were administered.

5.5.1 Risks of Examination Procedures

The procedures in this study are part of daily pediatric eye care practice in the United States and pose no known risks. As part of a routine usual-care exam, the patient may receive cycloplegic/dilating eye drops.

5.5.2 Adverse Events/Risks

The risks involved in the study are identical to those that would be present for a patient treated with the study treatment regimens who is not participating in the study.

5.5.3 Side Effects of Treatment

1. Atropine potentially could decrease the visual acuity in the sound eye, although this is almost always reversible. The diagnosis and management of reverse amblyopia is left to the investigator's judgment- see section 5.5.4.
2. Atropine could precipitate the development of an ocular deviation. See section 5.5.5.
3. Following atropine, local side effects of minimal severity include allergic lid reactions, local irritation, conjunctival hyperemia, and follicular conjunctivitis. Potential systemic side effects include dry skin and mouth, tachycardia, fever, flushing and irritability. These effects are very

507 uncommon using the dosage schedule in this protocol as noted in the previous studies of atropine
508 treatment. In ATS1,¹ among 204 patients, an ocular side effect was reported at least once for 26%
509 of patients, most commonly light sensitivity (18%), lid or conjunctival irritation (4%), and eye
510 pain or headache (2%). Facial flushing was reported for two patients, one of whom remained on
511 atropine with no further problems and one of whom was switched to homatropine. Atropine was
512 not discontinued because of side effects in any other patients. No other systemic side effects of
513 atropine were reported. Ocular side effects in ATS4, most commonly light sensitivity, were
514 reported by 13 patients (16%) in the daily group and 25 patients (29%) in the weekend group.⁴
515 However, these symptoms did not lead to a change in treatment. Facial flushing and fever were
516 reported for 2 patients in the daily group; one of these patients remained on atropine and the other
517 was switched to homatropine.

518
519 4. Atropine produces dilation of the pupil, which can increase the light that enters the eye. Although
520 it has not been demonstrated that atropine used for several months will have harmful ocular
521 effects, excessive exposure to light theoretically could be toxic to the retina. Atropine has been
522 used long-term to prevent the progression of myopia without an apparent adverse effect on
523 acuity.⁵⁻⁸ To minimize risks from pupil dilation, sunglasses, clip-ons, or flip-ups will be provided.
524 Hats with brims or visors will be encouraged.

525
526 5. When a patient develops adverse effects serious enough to discontinue atropine prior to the
527 primary outcome exam, the investigator should call the Protocol Chair to discuss the case. If
528 atropine is discontinued, then the patient could be switched to homatropine 5%. The following
529 guidelines should be followed after discussion with the Protocol Chair:

- 530 • If a patient has a serious systemic adverse effect of atropine (such as seizure), an
531 atropine-like drug should not be prescribed.
- 532 • If a patient has mild effects that may be due to atropine such as facial flushing, then
533 homatropine should be substituted. Initially, one drop is given. If there is no adverse
534 effect in three days, then a second drop is given. If there is no problem in three days,
535 then weekend homatropine is started. Drops should be administered in the morning.

536 537 **5.5.4 Reverse Amblyopia**

538 Atropine could decrease the visual acuity in the sound eye, although this is almost always reversible.
539 In ATS1, results were inconclusive as to whether atropine produced a transient decrease in sound eye
540 acuity. However, the results indicated that treatment did not cause a permanent reduction in sound eye
541 acuity. After two years of follow up, there was no difference in sound eye acuity between the two
542 treatment groups.

543
544 In ATS1, a reduction in sound eye visual acuity (2 or more lines) occurred at 6 months more frequently
545 when a plano lens was prescribed in addition to atropine (7 of 43, 16%) compared with treatment with
546 atropine alone (4 of 123, 3%; P=0.01). However, after longer follow-up the sound eye of only one
547 patient treated with atropine alone and no patient treated with atropine plus the plano lens was worse
548 than baseline.

549
550 The diagnosis and management of reverse amblyopia at each of the study visits is left to the
551 investigator's judgment. At all post-randomization visits (if indicated), a protocol will be followed for
552 re-testing and evaluating the sound eye if it has reduced vision (see section 4.4.3).

553

554 **5.5.5 Development of Strabismus**

555 The study treatment could precipitate the development of a new manifest ocular deviation (e.g.,
556 esotropia). If this occurs, the parent(s) will be advised to have the patient see the investigator as soon
557 as possible. If a new deviation is confirmed on examination, the decision as to whether to continue or
558 discontinue therapy will be left to the investigator. If amblyopia treatment is to be discontinued prior
559 to the primary outcome exam, then the Protocol Chair should be called to discuss the situation. The
560 development of a new heterotropia is an accepted risk of standard-care amblyopia therapy. However,
561 previous studies suggest that resolution of pre-existing strabismus during amblyopia treatment occurs
562 as often as development of new strabismus. In ATS1, new strabismus occurred in 13% of patching
563 patients and in 13% of those using atropine. Twenty-one percent of patients had resolution of their
564 preexisting strabismus with treatment. In ATS4, 10% of patients had a new strabismus or a worsening
565 of preexisting strabismus by ≥ 10 PD, and 8% were found to have resolution of preexisting strabismus
566 or reduction in their strabismic angle by ≥ 10 PD. The risk of developing strabismus in this study is no
567 greater than it would be with standard care of amblyopia.

568
569 Strabismus surgery is allowed at the discretion of the clinician if medically indicated following the 12-
570 week off-atropine outcome visit.

571
572 **5.5.6 Risk Assessment**

573 It is the investigators' opinion that the protocol's level of risk falls under DHHS 46.404 which is
574 research not involving greater than minimal risk.

575
576 **5.6 Reporting of Adverse Events**

577 Each investigator is responsible for informing his/her IRB of serious treatment-related adverse events
578 and for abiding by any other reporting requirements specific to his/her IRB.

579 Data on the complications of the study treatments will be tabulated regularly by the Coordinating
580 Center for review by the Data and Safety and Monitoring Committee. Serious, treatment-related
581 complications will be reported expeditiously to the Data and Safety Monitoring Committee, which will
582 receive a full adverse event report semi-annually. Following each DSMC data review, a summary will
583 be provided to IRBs.

584
585 **5.7 Patient Payments**

586 The parent/guardian of each patient will be compensated \$30 for each run-in phase follow-up visit, and
587 \$30 per visit for completion of the randomization visit, the primary outcome visit, and the 12-week off-
588 atropine outcome visit. For patients remaining in follow-up after the 12-week visit, \$30 will be paid
589 for each 10-week interval visit, up to an additional \$120 (4 exams). If there are extenuating
590 circumstances, additional funds may be provided for travel if expenses exceed \$30 and the patient will
591 be unable to complete the visit without reimbursement of travel expenses. All payments will be made
592 by the Jaeb Center in the month following the date of each completed visit.

593
594 **5.8 Study Costs**

595 The following will be provided by the study at no charge:

- 596 • Atropine eye drops.
- 597 • Non-prescription sunglasses or clip-on sunglasses if needed.
- 598 • Glasses if randomized to the atropine plus plano lens group.
- 599 • Reading glasses if needed for schoolwork.
- 600 • New lenses if the vision in the good eye worsens and the glasses prescription changes.

601
602
603
604
605
606
607
608
609
610
611
612
613
614
615
616
617
618
619
620
621

The study will pay for visits and testing that would not be done if the patient was not part of the study (research related visits). The patient or his/her insurance company will be responsible for the costs of visits that would be needed whether they were in the study or not (standard care visits).

5.9 Discontinuation of Study

The study may be discontinued by the Steering Committee (with approval of the Data and Safety Monitoring Committee) prior to the preplanned completion of enrollment and follow-up for all patients.

5.10 Contacts by the Jaeb Center for Health Research

The Jaeb Center serves as the PEDIG Coordinating Center. The Jaeb Center will be provided with the parent/guardian’s contact information. The Jaeb Center will maintain direct contact with the parents or guardian of each patient. Permission for such contacts will be included in the Informed Consent Form. The principal purpose of the contacts will be to develop and maintain rapport with the family and to help coordinate scheduling of the outcome examination. One phone contact is planned for each patient 5 weeks after randomization. Additional phone contacts will be made if necessary to facilitate the scheduling of the patient for follow-up visits. A patient newsletter, study updates, and a study logo item may be sent. Patients will be provided with a summary of the study results in a newsletter format after completion of the study by all patients.

Chapter 6: Sample Size Estimation and Statistical Analysis

The approach to sample size and statistical analyses are summarized below. A detailed statistical analysis plan will be written and finalized prior to the completion of the study. The analysis plan synopsis in this chapter contains the framework of the anticipated final analysis plan, which will supersede these sections when it is finalized.

6.1 Primary Analysis for Efficacy

The study is evaluating 2 management approaches for amblyopia in patients already treated with weekend atropine:

1. Continued weekend atropine 1%
2. Intensified treatment: Weekend atropine 1% with plano lens

The primary analysis will be a treatment group comparison of logMAR visual acuity scores obtained 10 weeks after randomization, adjusted for baseline acuity scores in an analysis of covariance (ANCOVA) model.

The primary analysis will follow the intent-to-treat principle. Data will be included only from patients who complete the 10-week outcome. There will be no imputation of data for patients who are lost to follow-up or withdraw from the study prior to the 10-week outcome. In a secondary analysis, imputation methods for missing data will be assessed (such as last-observation-carried-forward and multiple imputation) for consistency with the primary analysis. A separate analysis also will be conducted including only patients whose outcome exams were performed within the time window for the visit.

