80 When there has been no improvement with weekend atropine, eligible patients will be randomized to
81 one of two treatment regimens:

- 82 • Intensified treatment: Weekend atropine 1% with plano lens over the sound eye
83 • Control: Weekend atropine 1%
84

85 Sample Size

86 Seventy-nine patients will be randomized in each of the two treatment groups, for a total of 158
87 patients. This sample size has 90% power to detect a difference if the true difference in change from
88 baseline between groups is 0.075 logMAR at 10 weeks, with 2-sided type I error of 5%.
89

90 RCT Contact and Visit Schedule

- 91 • Phone call 5 weeks after randomization
92 • Primary outcome visit 10 weeks after randomization. Patients will return for an additional off-
93 atropine visit 2 weeks later.

- 94 • If amblyopic eye acuity improved by ≥ 1 line at primary outcome, follow-up visits at 10 week
95 intervals until no improvement, confirmed by a re-test
96

[figure not shown]
97 Primary Analysis

98 The primary outcome is amblyopic eye visual acuity 10 weeks after randomization.

99
100 The primary analytic approach for the amblyopic eye acuity will be a treatment group comparison of
101 the mean amblyopic eye acuity adjusted for baseline acuity using an analysis of covariance.
102

103 **1.4 Study Summary Flow Chart**

104

105

106

Chapter 2: Patient Enrollment

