3.1 Atropine Run-In Phase Follow-up Visits

After enrollment, weekend atropine is prescribed. Those children using daily atropine at enrollment will be switched to weekend atropine. During the run-in phase, follow-up visits will occur every 6 weeks as long as both of the following criteria are met:

- Amblyopic eye has improved at least one line from the previous visit
- Amblyopia is still present, defined as amblyopic eye acuity at least one line worse than the best sound eye acuity that has been recorded at any visit during the study

Note: If the amblyopic eye acuity meets the above criteria, follow-up will continue every 6 weeks even if the sound eye acuity has worsened from the prior visit.

At each follow-up visit, visual acuity will be tested using the ATS HOTV visual acuity testing protocol with a study certified visual acuity tester. If the amblyopic eye acuity has not improved from the prior visit, acuity should be re-tested.

- If on the re-test there is still no improvement from the prior visit, and the prior visit was at least six weeks ago and the patient was on atropine for at least 12 weeks then the patient has completed the Atropine Run-In Phase of the study, otherwise, the patient continues in follow-up.
- The better of the two amblyopic eye visual acuities at the last visit of the Atropine Run-In Phase serves as the baseline amblyopic eye acuity for the Randomized Trial.

If a re-test is required and acuity improves on the re-test, then the re-test acuity serves as the value to which the next visit is compared when judging improvement.

Patients may be enrolled into the Atropine Run-In Phase either at the initiation of atropine treatment or during the course of treatment, provided that the prescribed treatment regimen to that point has been weekend or daily atropine.

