4.2 New Spectacles Prescription upon Randomization

Patients randomized to the plano lens group will be given new, study-paid spectacles (frames and lenses) upon randomization. The amblyopic eye lens prescription will be identical to the current correction and the sound eye lens prescription will be "plano." The cost of any spectacle changes prior to randomization is not covered by the study.

The parents of children receiving new glasses with the plano lens will be encouraged to go to the study optician within 48 hours to have the glasses made. Every effort should be made to have the child wearing his/her new glasses within 4 days.

Parents of all patients randomized to the atropine plus plano lens group will be given a postage paid box to return the child's original pair of glasses to the site after they pick up the new glasses with the plano lens from the study optician. The site will return the original pair of glasses to the child at the

323 time of the 10-week primary outcome exam to wear between that exam and the off-atropine exam two
324 weeks later.

325

326 **4.3 Randomization of Eligible Patients**

- 327 1. Once a patient is randomized, that patient will be included in the analysis regardless of whether the
328 assigned treatment is received or not. Thus, the investigator must not randomize a patient until
329 he/she is convinced that the parent/guardian will accept and comply with either of the treatment
330 regimens. Regardless of whether the patient receives the assigned treatment or not, the patient is
331 still considered enrolled in the study and every effort should be made to perform the follow-up
332 examinations according to the study protocol.
- 333 2. The Jaeb Center will construct a Master Randomization List using a permuted block design
334 stratified by site and treatment at enrollment (weekend or daily atropine), which will specify the
335 order of treatment group assignments. A patient is officially enrolled when the website
336 randomization process is completed.

337

338 **4.3.1 Delay in Randomization**

- 339 1. Visual acuity testing and the ocular motility examination must be performed no more than 7 days
340 prior to randomization. If randomization is delayed beyond 7 days, then these tests must be
341 repeated to confirm eligibility and establish the baseline measures for the study.
- 342 2. No other parts of the examination (including the refraction) need to be repeated if they were

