700 atropine or weekend atropine versus weekend atropine with a plano lens over the sound eye for the
701 initial treatment of amblyopia. In ATS4, patients had office visits at 5 and 17 weeks following
702 randomization. In ATS8, patients had office visits at 5, 10, and 18 weeks following randomization.
703 Based on improvement in visual acuity among patients defined as stable, we assumed a standard
704 deviation for the change from baseline to 10-week outcome in this study of 0.14 logMAR. We will use
705 a two-sided alpha of 0.05, with 90% power to detect difference if the true difference in change from
706 baseline between groups is 0.075 logMAR at 10 weeks. With these assumptions, and accounting for
707 5% loss to follow-up, we have calculated a necessary total sample size of 158 patients.

708

709 A minimum of 158 patients are expected to be enrolled with a goal to enroll an appropriate
710 representation of minorities. As the enrollment goal approaches, sites will be notified of the end date
711 for recruitment. Patients who have signed an informed consent form can be randomized up until the
712 end date, which means the minimum recruitment goal might be exceeded. The maximum number of
713 randomized patients will be 178.

714

715 **6.5 Interim Analysis and Sample Size Re-estimation**

716 We are unaware of any previous literature reporting on the response to treatment of amblyopia still
717 present after initial treatment with weekend atropine. The sample size estimates above are based on a
718 study of the initial treatment of amblyopia and may not match our definition of no improvement in the
719 current study. Although we feel we have been conservative in our estimate of variation, a sample size
720 re-estimation will be performed once 50% of the originally planned number of patients have completed
721 the trial. A pooled estimate of variance without respect to treatment group will be calculated and used
722 to re-estimate sample size using a procedure that maintains masking.⁹ An adjustment will be made to
723 the final alpha based upon this interim sample size re-estimation.
724

Chapter 7: References

725
726
727
728
729
730
731
732
733
734
735
736
737
738
739
740
741
742
743
744
745
746

1. Pediatric Eye Disease Investigator Group. A randomized trial of atropine vs patching for treatment of moderate amblyopia in children. *Arch Ophthalmol* 2002;120:268-78.

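### The primary ANCOVA omits the weekend-or-daily atropine factor used to stratify the randomization; the analysis stays valid, but its standard error may be slightly conservative

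*Protocol*

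**What the plan says.** Section 4.3 of the protocol sets up a permuted-block list "stratified by site and treatment at enrollment (weekend or daily atropine"). The primary analysis is given twice with the same single covariate. The synopsis (1.3) compares "the mean amblyopic eye acuity adjusted for baseline acuity using an analysis of covariance", and section 6.1 has the 10-week logMAR score "adjusted for baseline acuity scores in an analysis of covariance (ANCOVA) model". The logistic analyses (6.2.1, 6.2.2) and the last-visit ANCOVA (6.2.2) also adjust for baseline acuity alone. Prior regimen returns only in 6.2.3, as an exploratory subgroup factor, and there it is the maximum prior treatment rather than treatment at enrollment. No reason is given for leaving the strata out of the models.

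The opening of Chapter 6 calls its content the "framework of the anticipated final analysis plan, which will supersede these sections when it is finalized".

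The sample size (6.4) assumes a standard "deviation for the change from baseline to 10-week outcome in this study of 0.14 logMAR", and claims no reduction for any covariate.

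On the stratum itself, section 3.1 says "Patients may be enrolled into the Atropine Run-In Phase either at the initiation of atropine treatment" or while treatment is under way. It treats enrollment as entry to the run-in, after which daily users move to weekend drops. Section 4.3 instead dates official enrollment to the completed web randomization.

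**The concern.** When arms are balanced on a factor by design and the model omits it, any outcome variance the factor explains stays in the error term. The treatment estimate has already gained from the balance, but the model-based standard error does not show it. The test is then somewhat conservative and the confidence interval somewhat wide. What is at stake is a little efficiency, together with agreement between the stated model and the design.

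The factor must also be codable. If enrollment means randomization, every patient who went through the run-in is on weekend atropine at that point, and only those who skip it (3.3) could be in the daily stratum. If it means run-in entry, a child starting atropine that day was on neither regimen beforehand, and no rule states the level.

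**Working it through.** **Reproducing the stated size.** Inputs from 6.4: difference 0.075, SD 0.14, two-sided alpha 0.05, power 90%, 5% loss.

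- Normal approximation: n per arm = 2 × (1.960 + 1.282)² × (0.14/0.075)² ≈ 73.2, rounded up to 74. Then 74/0.95 = 77.9, rounded up to 78, total 156.
- t-test: 74.2 per arm; 74.2/0.95 = 78.1, rounded up to 79, total 158. This is the protocol's figure.
- Power at 75 completers per arm (158 × 0.95 ≈ 150): SE = 0.14 × √(2/75) = 0.0229; 0.075/0.0229 − 1.96 ≈ 1.32, so 90.7% (90.3% by t-test).

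The stated power therefore needs nothing from the strata.

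**Closed-form gain.** Let R² be the share of residual variance that the factor explains (assumed; the protocol gives no value). Residual SD = 0.14 × √(1 − R²), with 75 per arm:

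| R² | SD | Power |
|---|---|---|
| 0 | 0.1400 | 90.7% |
| 1% | 0.1393 | 90.9% |
| 2% | 0.1386 | 91.2% |
| 5% | 0.1365 | 92.0% |
| 10% | 0.1328 | 93.3% |

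This slightly overstates the gain, because the unadjusted estimate already benefits from stratified balance.

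**How strong is 5%?** If 25% are in the daily stratum (assumed), the implied difference between strata is √(R² × 0.14² / (0.25 × 0.75)). At R² = 5% this is √(0.00098/0.1875) = 0.072 logMAR, about the whole target treatment effect. At 10% it is 0.102 logMAR.

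**Simulation with baseline acuity in the model.** 150 patients, blocks of 4, 30% on daily atropine, 2,000 replicates per setting, all assumed. Monte Carlo error is about 0.7 points for power and 0.5 for type I error. Power by model:

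| Sites | Variance share: site / regimen | Baseline only | + regimen | + regimen and fixed sites |
|---|---|---|---|---|
| 20 | 0 / 0 | 88.95% | 88.95% | 88.25% |
| 20 | 5% / 2% | 89.35% | 89.65% | 90.0% |
| 20 | 10% / 5% | 90.75% | 92.2% | 92.5% |
| 50 | 0 / 0 | 88.95% | 89.2% | 83.6% |
| 50 | 5% / 2% | 90.9% | 91.1% | 83.8% |
| 50 | 10% / 5% | 91.0% | 91.45% | 87.9% |

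The regimen term adds 0 to about 1.5 points. Relative to baseline only, fixed site effects range from −0.7 to +1.75 points with 20 sites and lose 3.1 to 7.1 points with 50.

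Under no treatment effect the baseline-only model rejected in 3.6% to 5.1% of replicates. The mild conservatism shows in the 20-site, 10%/5% null setting: the mean model SE was 0.0228 against an actual SD of the estimate of 0.0216.

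**Stronger assumed regimen effect.** A second simulation (40 sites, 25% daily, blocks of 4, no baseline covariate) gave 89.7% to 91.4% at R² = 5% and 90.8% to 93.1% at 10%, gains of 1.7 and 2.3 points.

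**The case against.** The strongest reply is that covariate lists belong in the analysis plan, which will replace Chapter 6 and is not shown. That stands as a reason for low weight, since the matter may already be settled there. It does not remove the point: the protocol does not leave the covariates open but names them, in the synopsis and again in 6.1, and they do not match its own randomization.

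The second reply is that nothing shows the stratum to be prognostic. This is right. Section 4.3 gives no reason for the choice. Patients must have stopped improving before randomization, and their baseline acuity after that treatment is already in the model. A reader might infer that the trial stratified on a known predictor and then gave away precision by dropping it. The documents do not support that flat claim, because they give neither the factor's prognostic strength nor the number of sites.

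A reader might also infer that every omitted stratum costs precision in every model. For site, the table shows that fixed effects can lose power. In the logistic models, adding a prognostic covariate generally raises the standard error of the log odds ratio and changes what that ratio measures. Any benefit there would be in power, which was not computed.

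On the stratum wording, it is fair to read a child starting atropine as weekend, since that is what 3.1 prescribes after enrollment. The unclear wording carries none of the power difference. It matters only because the analysis factor has to equal the randomization factor.

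**Conclusion.** The mismatch between the stratified design and the stated primary model is real but minor. Validity, type I error and the planned size are not threatened. Adding the two-level regimen factor would change power by about 0 to 2 points, with 2.3 the largest simulated value, if it explains 0 to 10% of residual variance. The upper half of that range already needs a stratum difference as large as the treatment effect sought. The figures rest on assumed site numbers, daily share and block size. The simulation behind the top of the range left out baseline acuity, and a random site intercept was not tested. The case for the change is that it is nearly free and aligns the analysis with the design, not that the present plan fails.

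**What to change.** - **6.1 and the last-visit ANCOVA in 6.2.2:** state that the model adjusts for baseline acuity and for treatment at enrollment (weekend or daily), coded as in the randomization. The synopsis in 1.3 should match. Cost: one line and one degree of freedom. If the sponsor prefers to omit the factor, a sentence should say why.
- **Site:** do not add one fixed effect per site. A random intercept or pooled small sites is optional.
- **Logistic models in 6.2.1 and 6.2.2:** the same factor may be added for consistency with the design, with no claim of a smaller standard error.
- **3.1 and 4.3:** reconcile the two uses of enrollment so that the stratum refers to one time point, and state the level for a patient who starts atropine at that point. Cost: one or two sentences. If randomization has already begun, describe the coding actually used.
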